## PROTOCOL SYNOPSIS

### Title of Study:

An Open-label and Single Arm Study of ATG-010 in Patients with Relapsed or Refractory Diffuse Large B-Cell Lymphoma (DLBCL)

### Indication

Relapsed or Refractory DLBCL

### Objectives

#### Primary Objective:

To determine the overall response rate (ORR) of ATG-010 evaluated by central radiological review in relapsed or refractory DLBCL subjects who have at least 2 but no more than 5 previous systemic regimens.

#### Secondary Objectives:

- To determine the ORR evaluated by investigator
- To determine the duration of response (DOR) evaluated by central radiological review
- To determine the disease control rate (DCR) evaluated by central radiological review
- To determine the median overall survival (OS)
- To determine the median progression-free survival (PFS)
- To determine the PFS, ORR, DOR, DCR, and OS in subjects with “double hit” DLBCL (DH-DLBCL) and non-DH-DLBCL; in subjects with GCB and non-GCB DLBCL; as well as with “very good”, “good”, and “poor” Revised International Prognostic Index (R-IPI)
- To assess the safety and tolerability of ATG-010

### Background and Study Rationale

#### Study Background

DLBCL is an aggressive cancer with current immunochemotherapy, 60 to 65% of patients are progression-free at 5 years, but the remaining about 1/3 of patients with DLBCL have a poor prognosis with disease resistant to available agents. A very clear unmet medical need persists for patients with relapsed or refractory DLBCL.

#### Study Rationale:

ATG-010 (Selinexor) is an orally bioavailable selective inhibitor of nuclear export (SINE) compound that specifically blocks exportin 1 (XPO1). Preclinical studies showed that ATG-010 can lead to the nuclear accumulation and re-activate of tumor suppressor proteins and other growth modulators, promote rapid onset of apoptosis both *in vitro* and *in vivo* of hematological and solid tumor cells; meanwhile it has little effect on normal cells. SADAL is an international, multicenter, open IIb, ongoing study. As of 15 November 2018, the efficacy data (Karyopharm, 2018) for SADAL Study were updated and ORR was 29.6% by central radiology laboratory based on 115 subjects in modified intent-to-treat (mITT) population, including CR 9.6% and PR 20.0%; the median DOR was 9.2 months in all ATG-010 responders

(total 34 subjects; 11 CRs+23 PRs), median DOR in CR subjects was 23 months, and median DOR in PR subjects was 7.8 months. The median OS was 9.1 months in all subjects, 29.7 months for CR/PR subjects, but only 3.2 months for progressive disease/not reached (PD/NR) subjects. These results showed the correlation between tumor responses of DLBCL and clinical efficacy of treatment, the OS observed in ATG-010 non-responders with PD/NR was also consistency with published references.

Based on the encouraging clinical efficacy and safety data obtained by ATG-010 monotherapy in the treatment of subjects with recurrence or refractory DLBCL, FDA granted the rapid channel of ATG-010 monotherapy for recurrence or refractory DLBCL on 07 November 2018, aiming at accelerating the clinical study and marketing approval of ATG-010.

According to the efficacy data obtained by SADAL Study in the population of relapse or refractory DLBCL subjects in the west, the current study plans to verify the clinical efficacy of ATG-010 single drug treatment in subjects with relapse/refractory DLBCL who have received no more than 5 systematic treatment regimens in the past.

### **Study Design**

This is an open-label, single arm, and registered study. About 60 subjects with relapsed or refractory DLBCL plan to be enrolled in about 10 study sites of the study. It is planned that at least 50% (~30 subjects) will have the GCB subtype of DLBCL. Enrolled subjects will be treated with a fixed dose, 60 mg of ATG-010, orally, twice weekly, each 4-week a cycle. Subjects should remain on the study treatment of ATG-010, until either PD or occurrence of unacceptable toxicity.

Confirmed evidence of DLBCL progressive or failed to the last treatment regimen is required for study entry, and subjects must have measurable disease at screening per the Lugano criteria for response assessment (Cheson, 2014).

Disease assessment (tumor measurement) will be made by PET-CT and Contrast-enhanced CT (Tumor measurement) at screening (within the first 14 days of Cycle 1 Day 1), enhanced CT should include the neck, chest, abdomen, pelvic cavity (including the inguinal/femoral region), if clinically indicated, as well as other anatomical sites. If CT is contraindicated, MRI scan will be performed. PET-CT and contrast-enhanced CT scans will be performed on Cycle 3 Day 1 ( $\pm$  1 week) and then every 8 $\pm$  weeks (ie, Day 1 of odd numbered cycles) until disease progression is confirmed by the central radiological review. The PET-CT is allowed at alternating assessment time points (ie, every 16 weeks, or every other scan) if PET-CT cannot be performed for every assessment. If CT scan suggests the possibility of obtaining CR, PET-CT should be performed for confirmation. Results of PET-CT and contrast-enhanced CT scans performed beyond a predetermined time point should be recorded on the eCRF and images of all disease assessment scans performed during the study period will be provided to the central radiological review.

Bone marrow aspirates and/or biopsies will be taken within 1 month prior to first dose (baseline) to assess bone marrow involvement. The bone marrow biopsy will be repeated whenever clinically indicated to confirm CR in only those subjects who had DLBCL with known bone marrow involvement prior to dosing.

## **Diagnosis and Main Criteria for Inclusion: Inclusion Criteria**

To be included in this study, a patient must meet all the following criteria:

1. The patient must provide informed consent form (ICF) prior to the first screening procedure.
2. Age  $\geq 18$  years.
3. ECOG performance status of  $\leq 2$ .
4. Subjects should have estimated life expectancy of  $>3$  months at study entry.
5. Previously treated, pathologically confirmed *de novo* DLBCL, or DLBCL transformed from previously diagnosed indolent lymphoma (e.g., follicular lymphoma).
6. Subjects must have received at least 2 but no more than 5 previous systemic regimens for the treatment of DLBCL, including at least 1 course of anthracycline-based chemotherapy (unless absolutely contraindicated due to cardiac dysfunction, in which case other active agents must have been given, such as etoposide, bendamustine, or gemcitabine, etc.) and at least 1 course of anti-CD20 immunotherapy (e.g., rituximab), unless contraindicated due to severe toxicity. Subjects who were considered ineligible for standard multi-agent immunochemotherapy must have received at least 2 and no more than 5 prior treatment regimens including at least 1 course of anti-CD20 antibodies and must be approved by the Medical Monitor. Prior stem cell transplantation is allowed. Induction, consolidation, stem cell collection, preparative regimen, and transplantation  $\pm$  maintenance are considered a single line of therapy.
7. Documented evidence of DLBCL progressive (PD) or failed (SD) to the last treatment regimen.
8. Subjects must have measurable disease per the Lugano criteria for response assessment of lymphoma (Cheson, 2014).
9. Subjects must not be eligible for high-dose chemotherapy with autologous stem cell transplantation rescue, ie, meet any of the following criteria:
  - a. Age  $\geq 65$  years old.
  - b. Existed severe organ dysfunction or complications.
  - c. Failed to obtain PR or CR through salvage therapy.
  - d. Failure of stem cell collection.
  - e. Subjects refuse to receive high-dose chemotherapy with autologous stem cell transplantation.
10. Female subjects of child-bearing potential must have a negative serum pregnancy test at screening (Female subjects of child-bearing potential is defined as female whose menstruation has begun, who are not in the late menopause, and who have not received surgical sterile [e.g., hysterectomy, bilateral tubal ligation, bilateral oophorectomy]). Post-menopausal period is defined as successive amenorrhea  $\geq 12$  months without specific reason. Female subjects of child-bearing potential must agree to use reliable

methods of contraception for 3 months after their last dose of medication.

11. Male subjects (including those who have undergone vasectomy) must agree to use condoms if sexually active with a female of child-bearing potential and must agree that they have no plan to make their female partners pregnant during the use of study drug and within 3 months after the last dose of medication since they signed ICF.

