### **Exclusion Criteria**

Subjects meeting any of the following exclusion criteria are not eligible to enroll in this study.

1. Subjects who are pregnant or lactating.
2. DLBCL with mucosa-associated lymphoid tissue (MALT) lymphoma, composite lymphoma (Hodgkin's lymphoma + non-Hodgkin's lymphoma[NHL]), or DLBCL transformed from diseases other than indolent NHL.
3. Primary mediastinal (thymic) large B-cell lymphoma.
4. Known central nervous system lymphoma or meningeal involvement.
5. Subjects whose most recent systemic anticancer therapy include radiation, chemotherapy, immunotherapy, radio-immunotherapy, or any other anticancer therapy other than glucocorticoids within 4 weeks prior to first dose of study drug.
6. Subjects who have not recovered to Grade  $\leq 1$  clinically significant adverse events, or to their baseline, except for the hair loss, from their most recent systemic anti-DLBCL therapy.
7. Subjects with active graft-versus-host disease after allogeneic stem cell transplantation. At least 4 months prior to first dose of study drug must have elapsed since completion of allogeneic stem cell transplantation.
8. Major surgery within 2 weeks of first dose of study treatment of ATG-010.
9. Any life-threatening illness, medical condition, or organ system dysfunction which, in the Investigator's opinion, could compromise the patient's safety.
10. Unstable cardiovascular function:
  - a. Symptomatic ischemia, or
  - b. Uncontrolled clinically significant conduction abnormalities (ie, ventricular tachycardia on anti-arrhythmia is excluded; First degree atrioventricular block or asymptomatic left anterior fascicular block /right bundle branch block will not be excluded), or
  - c. Congestive heart failure of New York Heart Association Class  $\geq 3$ , or
  - d. Myocardial infarction within 3 months.
11. Uncontrolled (ie, clinically unstable) infection requiring parenteral antibiotics, antivirals, or antifungals within 1 week prior to first dose; however, prophylactic use of these agents is acceptable even if parenteral.
12. Active hepatitis B virus (HBV) or hepatitis C virus (HCV)infection.
  - a. Serological positive for hepatitis B surface antigen (HBsAg) or hepatitis B core antibody (HBcAb). Subjects who are HBcAb positive but HBsAg negative can be

enrolled if HBV-DNA cannot be detected. The upper limit of normal HBV-DNA testing is based on the test value of each site.

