#### **Test Product, Dose and Mode of Administration:**

The dosage regimen of ATG-010 specified as follow: Subjects will be administered as a fixed oral ATG-010 of 60 mg twice weekly (e.g., Monday and Wednesday or Tuesday and Thursday, etc.) on Weeks 1-4 of each 4-week cycle (total of 8 doses per cycle).

Subjects who achieved partial response (obtained the expected best efficacy judged by

investigator) or better response will transition to maintenance dosing until either PD or occurrence of unacceptable toxicity.

The maintenance dose of ATG-010 will be 60 mg orally QW. Subjects whose dose has been reduced such that the total weekly dose is <60 mg will continue that tolerated dose. If a patient experiences a subsequent increase in disease burden, or per the discretion of the Investigator, the dose of ATG-010 can be increased to 60 mg orally twice weekly, after discussion with the Medical Monitor.

If more than one different type of toxicity occurs concurrently, the most severe grade will determine the modification. All subjects who have a treatment delay of more than 28 days due to drug-related adverse events will withdraw from the study treatment. Each dose modification or treatment delay must be documented in the eCRF, including the respective reason.

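### Inclusion item 10 of the synopsis states a contraception period for women that begins only after the last dose and does not mention the treatment period

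*Combined protocol and SAP*

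**What the plan says.** Item 10 of the Inclusion Criteria in the synopsis first requires a negative serum pregnancy test at screening and defines child-bearing potential. It then sets the contraception duty in one sentence, which begins "Female subjects of child-bearing potential must agree to use reliable" and continues "methods of contraception for 3 months after their last dose of medication". It gives no start point other than the last dose.

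Item 11, for men, contains a condom commitment and a commitment not to plan a pregnancy with a partner. It ends with a period that runs "during the use of study drug and within 3 months after the last dose of medication since they signed ICF".

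Treatment has no fixed length. Under Study Design, "Subjects should remain on the study treatment of ATG-010, until either PD or occurrence of unacceptable toxicity". Under Test Product, Dose and Mode of Administration, subjects with a partial response or better "will transition to maintenance dosing until either PD or occurrence of unacceptable toxicity".

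Three other provisions concern pregnancy:

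- Exclusion criterion 1 bars "Subjects who are pregnant or lactating".
- Footnote 18 to Table 1 calls for a serum test within 3 days before the first dose and at the End of Treatment Visit, with urine tests on Day 1 of Cycle 2 and of each later even-numbered cycle.
- The Discontinuation Criteria require the investigator to take a pregnant patient off study treatment.

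**The concern.** Item 10 is an eligibility rule, so what a woman agrees to under it is a condition of entry. Read as worded, she can meet it by agreeing to contraception once she has stopped the drug, with no commitment for the time she is taking it. That is the time when a pregnancy would be directly exposed to ATG-010.

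The matter at stake is fetal safety and the clarity of an eligibility rule to be applied at about 10 sites. It has no bearing on the primary endpoint, the power statement, the sample size or any analysis population.

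**Working it through.** The plan gives no figure on this point, so the check compares the texts.

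**Step 1: the period in item 10.** The sentence has one duty (reliable contraception) and one period (three months counted from the last dose). Nothing in it says during treatment, throughout, or until. The stated period therefore runs from the last dose to the last dose plus 3 months.

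**Step 2: the period of exposure.** Dosing runs from Cycle 1 Day 1 to progression or unacceptable toxicity, and maintenance dosing has the same end point. The period before the last dose is therefore open-ended, and item 10 does not mention it.

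**Step 3: whether other text fills the gap.**

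| Provision | When it acts | What it does | Requires contraception during dosing? |
|---|---|---|---|
| Item 10, serum test | Screening | Screens for pregnancy | No |
| Exclusion criterion 1 | Entry | Excludes existing pregnancy or lactation | No |
| Table 1, footnote 18 | Before first dose, Cycle 2 and later even cycles, end of treatment | Detects pregnancy | No |
| Discontinuation Criteria | After pregnancy is known | Stops treatment | No |

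Testing cannot stand in for prevention. From Cycle 2 onward the scheduled urine tests are two cycles apart, which is 2 × 4 = 8 weeks. A pregnancy found at one of these tests may already have been exposed.

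**Step 4: what item 11 adds.** Item 11 names the time on study drug; item 10 does not. Grammatically, that period attaches most directly to the commitment not to plan a pregnancy, and the condom commitment before it has no clear period of its own. Item 11 is therefore evidence that the authors had the treatment period in mind. It is not a cleanly drafted parallel rule from which item 10 departs.

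**Step 5: whether words were lost in conversion from PDF.** The break in item 10 falls between 'reliable' and 'methods'. The sentence reads straight across it. A phrase about the treatment period would belong later, after 'contraception', where the line is unbroken. There is no sign of a redaction or gap.

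**The case against.** The strongest reply is that nobody would apply item 10 literally. The plan excludes pregnancy at entry, tests for it repeatedly on treatment and stops treatment if it occurs. In that setting, three months after the last dose reads naturally as the end of a duty already in force, since a duty that begins only when exposure ends would make little sense. This stands as evidence of intent, and it makes a harmful literal reading unlikely. It does not change what the item says, and an eligibility criterion should not depend on readers supplying missing words.

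The second reply is that this is a synopsis. It refers to appendices that are not in the supplied text (Appendices 1, 5 and 6), so a fuller document exists, and the consent pages have been removed. Either could state the full period. This also stands, and it limits the point to the synopsis wording.

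Four stronger readings are tempting, and the documents do not support them:

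- A reader might infer that women in the trial actually go without required contraception during dosing. That cannot be concluded without the protocol body and consent form.
- A reader might infer that men have a complete on-treatment contraception rule and women have none. Item 11 is too loosely drafted for that contrast.
- A reader might count scheduled doses falling outside the stated period and present the count as the size of the problem. Such a count is settled by definition, because no dose can follow the last dose. It adds no evidence and measures no risk.
- A reader might conclude that the duty for women must start at consent. The defect shown is the missing treatment period; a start at consent would be a separate choice.

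**Conclusion.** Item 10 is wrong as written, and very likely through a drafting omission. It is the only text in the synopsis and schedule of assessments that sets a contraception period for women, and it leaves out the open-ended time on drug.

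No numerical size can be given. The documents do not report how many of the roughly 60 subjects will be women of child-bearing potential, and no estimate is offered. There is no effect on the response rate, power, sample size or analysis. The point should be corrected because it is a safety-related entry condition and the correction is simple.

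The conclusion assumes that the supplied synopsis text is complete at this sentence, which its continuous reading supports. It makes no claim about the protocol body or the consent form.

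**What to change.** In item 10, insert 'during study treatment and' immediately before the words that give the three-month period, so that the duty covers both the time on drug and the three months after it. Then check that the protocol body and the consent form state the same period, and align whichever differs.

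The cost is four words and a consistency check. The design, visit schedule, assessments, analysis and sample size do not change.

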### **Exclusion Criteria**

Subjects meeting any of the following exclusion criteria are not eligible to enroll in this study.

1. Subjects who are pregnant or lactating.
2. DLBCL with mucosa-associated lymphoid tissue (MALT) lymphoma, composite lymphoma (Hodgkin's lymphoma + non-Hodgkin's lymphoma[NHL]), or DLBCL transformed from diseases other than indolent NHL.
3. Primary mediastinal (thymic) large B-cell lymphoma.
4. Known central nervous system lymphoma or meningeal involvement.
5. Subjects whose most recent systemic anticancer therapy include radiation, chemotherapy, immunotherapy, radio-immunotherapy, or any other anticancer therapy other than glucocorticoids within 4 weeks prior to first dose of study drug.
6. Subjects who have not recovered to Grade  $\leq 1$  clinically significant adverse events, or to their baseline, except for the hair loss, from their most recent systemic anti-DLBCL therapy.
7. Subjects with active graft-versus-host disease after allogeneic stem cell transplantation. At least 4 months prior to first dose of study drug must have elapsed since completion of allogeneic stem cell transplantation.
8. Major surgery within 2 weeks of first dose of study treatment of ATG-010.
9. Any life-threatening illness, medical condition, or organ system dysfunction which, in the Investigator's opinion, could compromise the patient's safety.
10. Unstable cardiovascular function:
  - a. Symptomatic ischemia, or
  - b. Uncontrolled clinically significant conduction abnormalities (ie, ventricular tachycardia on anti-arrhythmia is excluded; First degree atrioventricular block or asymptomatic left anterior fascicular block /right bundle branch block will not be excluded), or
  - c. Congestive heart failure of New York Heart Association Class  $\geq 3$ , or
  - d. Myocardial infarction within 3 months.
11. Uncontrolled (ie, clinically unstable) infection requiring parenteral antibiotics, antivirals, or antifungals within 1 week prior to first dose; however, prophylactic use of these agents is acceptable even if parenteral.
12. Active hepatitis B virus (HBV) or hepatitis C virus (HCV)infection.
  - a. Serological positive for hepatitis B surface antigen (HBsAg) or hepatitis B core antibody (HBcAb). Subjects who are HBcAb positive but HBsAg negative can be

enrolled if HBV-DNA cannot be detected. The upper limit of normal HBV-DNA testing is based on the test value of each site.

- b. HCV antibody positive. But subjects with positive HCV antibodies can be enrolled if HCV-RNA cannot be detected.

13. Known human immunodeficiency virus (HIV) infection.

14. Subjects unable to swallow tablets, subjects with malabsorption syndrome, or any other gastrointestinal disease or gastrointestinal dysfunction that could interfere with absorption of study treatment of ATG-010.

15. Any of the following laboratory abnormalities (without corrective treatment)

- a. Absolute neutrophil count <1000 cells/mm^3 or platelet count <75,000/mm^3 during screening and on C1D1. Platelet infusions within 1 week prior to the first study treatment and/or use of granulocyte-stimulating factors and platelet growth factors 2 weeks prior to the first study treatment
- b. A circulating lymphocyte count of >50,000/ $\mu$ L
- c. Hepatic dysfunction: bilirubin >2.0 times the upper limit of normal (ULN) (except subjects with Gilbert's syndrome: total bilirubin of > 3×ULN) and alanine aminotransferase (ALT) and aspartate aminotransferase (AST) >2.5 ×ULN. In subjects with known liver involvement of their DLBCL, AST and ALT >5 ×ULN
- d. Severe renal dysfunction: estimated creatinine clearance of <30 mL/min, measured in 24-hour urine or calculated using the formula of Cockcroft and Gault (can refer to Appendix 5)
- e. Hematopoietic dysfunction: hemoglobin <10.0 g/dL within 14 days of and including C1D1 and/or subjects receiving red blood cell transfusion within 14 days of and including C1D1.

16. Subjects with a body surface area <1.4 m^2 (can refer to Appendix 6).

17. Psychiatric illness or substance use that would prevent the patient from giving informed consent or being compliant with the study procedures.

#### **Duration of Study:**

The enrollment period for the study is expected to be 6 months, the end of study will be defined as 12 months after the last patient enrolled in the study, has withdrawn consent, has died, or has been lost to follow-up, (whichever occurs first). In addition, Sponsor may at any time decide to discontinue the study for reasons including but not limited to security.

Upon completion of this study, Sponsor will provide continuous treatment (as determined by the investigator) to the subjects who still have clinical benefits. The study drug may be provided through additional extension studies or in other forms at the discretion of the Sponsor.

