### **Statistical Summaries:**

The primary endpoint analyses will be conducted after at least one efficacy evaluation following the enrollment of the last patient to the study (including efficacy and safety), and the amended analyses on efficacy and safety will be conducted after the End of Study.

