- 21 Disease assessment (tumor measurement) will be made by PET-CT and Contrast-enhanced CT (Tumor measurement) at screening (within the first 14 days of Cycle 1 Day 1), enhanced CT should include the neck, chest, abdomen, pelvic cavity (including the inguinal/femoral region), if clinically indicated, as well as other anatomical sites. If CT is contraindicated, MRI scan will be performed. PET-CT and contrast-enhanced CT scans will be performed on Cycle 3 Day 1 ( $\pm 1$  week) and then every 8 $\pm 1$  weeks (ie, Day 1 of odd numbered cycles) until disease progression is confirmed by the central radiological review. The PET-CT is allowed at alternating assessment time points (ie, every 16 weeks, or every other scan) if PET-CT cannot be performed for every assessment. If CT scan suggests the possibility of obtaining CR, PET-CT should be performed for confirmation. Results of PET-CT and contrast-enhanced CT scans performed beyond a predetermined time point should be recorded on the eCRF and images of all disease assessment scans performed during the study period will be provided to the central radiological review.
- 22 Disease status will be assessed by the Lugano criteria for response assessment of lymphoma (*Cheson, 2014; Appendix 1*) on Cycle 3 Day 1 ( $\pm 1$  week) and then every 8 weeks  $\pm 1$  week (ie, Day 1 of odd numbered cycles) until disease progression is confirmed by the central radiological review.
- 23 Bone marrow aspirates and/or biopsies will be taken within 1 month prior to first dose (baseline) to assess DLBCL involvement in bone marrow. The bone marrow biopsy will be repeated whenever clinically indicated to confirm CR in only those subjects who had DLBCL known bone marrow involvement prior to dosing.
- 24 To minimize nausea, all subjects should receive 5-HT3 antagonists (8 mg or equivalent) unless contraindicated, starting on Cycle 1 Day 1 before the first dose of ATG-010 and continued 2 to 3 times daily thereafter, as needed. Olanzapine is also recommended for the first 8 weeks, after which the dosage can be gradually reduced according to the situation of patient.
- 25 ATG-010 dosing will occur on Days 1 and 3 of Weeks 1-4 of each 4-week cycle. For doses on non-clinic days, the patient will be provided doses to take home.

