- 26 Phone call to evaluate supportive care medications and adverse events, and to adjust supportive care as appropriate. In Cycle 1, the telephone contact with the patient must take place on Day 3 (+ 1 day) following the Cycle 1 Day 1 of ATG-010 dosing. For Cycles  $\geq 2$ , this phone call will be made on Day 10 (+ 1 day) and 24 (+ 1 day), corresponding to Day 3 (+ 1 day) of every week in which a clinic visit does not occur.
- 27 By phone (or a visit, if possible), assess patient status, follow-up on any adverse events that were not resolved at the End of Treatment Visit, and information on any antineoplastic therapies utilized since discontinuation of study treatment.

28 After treatment discontinuation, a call will be made to the patient (or the patient's family) every 3 months ( $\pm$  14 days) from the date their last dose until the End of Study to determine the patient's survival status and information on any antineoplastic therapies utilized since discontinuation of study treatment.

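### Could the end-of-study sentence let one patient's death close survival follow-up early for the patients still alive?

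*Combined protocol and SAP*

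**What the plan says.** The Duration of Study section of the synopsis gives the accrual time, "The enrollment period for the study is expected to be 6 months", and then the closing rule: "the end of study will be defined as 12 months after the last patient enrolled in the study, has withdrawn consent, has died". Loss to follow-up completes the list, and a tie-break in parentheses takes whichever event comes earliest.

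The End of Study is used in two other places:
- Statistical Summaries places the primary analysis after at least one efficacy evaluation following the last enrolment. It then says that "the amended analyses on efficacy and safety will be conducted after the End of Study".
- Footnote 28 of Table 1 has survival calls every 3 months, "from the date their last dose until the End of Study to determine the patient's survival status".

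The Secondary Objectives include "To determine the median overall survival (OS". Footnotes 21 and 22 of Table 1 tie tumour assessment to each patient's own course, "until disease progression is confirmed by the central radiological review", with no mention of the End of Study.

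**The concern.** The only grammatical subject in the closing rule is the last patient, in the singular. The sentence then lists that patient's enrolment, withdrawal, death and loss, and takes the earliest. One literal reading is that the study ends 12 months after last enrolment, or sooner if that same patient dies, withdraws or is lost.

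Survival calls stop at the End of Study and the amended analyses follow it, so on this reading one patient's outcome would set the OS cut-off for every patient still alive and in follow-up. In a disease with a reference median OS of 9.1 months, an early trigger would be more likely than not. Median OS is a stated objective and the trial is meant for registration, so a cut-off left to chance would matter if that were the rule.

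**Working it through.** **Step 1: the possible readings**

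| Reading | End of Study | Follow-up lost |
|---|---|---|
| A | 12 months after last enrolment, or the last enrolled patient's own death, withdrawal or loss if earlier | Yes, for patients still alive and followed |
| B | 12 months after the earliest listed event; enrolment always comes first, so 12 months after last enrolment | None |
| C | 12 months after last enrolment, or when the last patient still in follow-up has died, withdrawn or been lost, if earlier | None |

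Reading B leaves the later clauses idle. Readings A and C both give every clause, and the tie-break, some work to do. Grammar therefore does not favour A over C.

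**Step 2: what the rest of the document implies**

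Statistical Summaries sets out a primary analysis after the last patient's first efficacy evaluation and then an amended analysis after the End of Study. That order presumes that the End of Study comes later. The first scheduled scan is at Cycle 3 Day 1, which is 8 weeks. Under A, with the Step 3 assumptions, the study would end before that scan with probability 1 − exp(−0.07617 × 56/30.4375) = 0.131. Three-monthly survival calls and a median OS objective also suit a set follow-up period better than a stop triggered by one patient. None of this strictly excludes A, but all of it points away from A.

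**Step 3: the size, under reading A only**

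Inputs from the document: N = 60 (Study Design), 6-month accrual (Duration of Study) and the reference-study figure "The median OS was 9.1 months in all subjects, 29.7 months for CR/PR subjects" (Study Rationale). Assumptions: exponential OS, uniform accrual, no withdrawal or loss (no rate is given), and medians of 6 and 12 months as a range.

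- Hazard: λ = ln 2 / 9.1 = 0.07617 per month.
- Chance that the last patient dies within 12 months: 1 − 0.5^(12/9.1) = 0.599.
- Mean time from last enrolment to end: 0.599 / 0.07617 = 7.9 months instead of 12.
- Expected deaths with a fixed end, taking potential follow-up as uniform on 12 to 18 months: 60 × [1 − (exp(−12λ) − exp(−18λ)) / (6λ)] = 60 × [1 − (0.4009 − 0.2538) / 0.4570] = 40.7. Simulation gives about 40.5.

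Simulation of 20,000 trials per setting (Kaplan-Meier median):

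| True median OS (months) | Early end under A | Mean deaths, A vs fixed | Median not reached, A vs fixed |
|---|---|---|---|
| 6 | 75% | 37 vs 49 | 10% vs 0% |
| 9.1 | 60% | 32 vs 40.5 | 23% vs 0.1% |
| 12 | 50% | 28 vs 34.5 | 32% vs 4% |

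The survival shape matters little. A mixture with 29.6% responders at median 29.7 months and the rest at 6.35 months, which keeps the overall median at 9.1, gives early end 59%, deaths 31 vs 39, and median not reached 24% vs 0.3%. An assumed 5% to 10% withdrawal or loss by 12 months raises the 60% to 62% to 64%. Under B or C the fixed-end figures apply.

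**Step 4: what kind of loss it would be**

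Under A the cut-off depends on one patient's event time, which is independent of the other 59 patients' survival. For them the censoring is in effect administrative, so the Kaplan-Meier curve is not materially biased; it is shorter and less precise. Patients already dead lose nothing. Any effect on progression-free survival and duration of response would be indirect, through study closure.

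The plan's one design calculation is untouched. With N = 60 and true response rate 28.3%, the smallest count above 20.7% is 13 (13/60 = 21.7%), and P(X ≥ 13) = 0.903, which matches the stated power of more than 90%. It does not involve the End of Study date.

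**The case for a change.** The best case for acting is that the date is operative, nothing elsewhere defines it better, and one sentence would settle it at no cost: no more patients, visits or scans. Reading A is not strained, because the sentence never says all patients, and reading C needs words that are not on the page. If A were applied, a study meant for registration could close with its median OS not estimable.

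Much of this stands. The wording is defective, the date does govern the OS cut-off, and the figures are right for reading A. What does not stand is the step from unclear wording to a likely wrong result. Nothing shows that the sponsor chose a single-patient stop, and the analysis order sits badly with one. A clearer sentence would restate reading C, so under the likely conduct of the trial it would alter no data and no estimate.

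**Conclusion.** The sentence is unclear, but no change is needed. Its most plausible meaning is 12 months after the last enrolment, or earlier only if nobody remains in follow-up. On that meaning, about 40 to 41 deaths are expected at a median of 9.1 months and the Kaplan-Meier median is reached in 99.9% of simulated trials.

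The harmful reading is the least plausible of the three. Even then the median would still be reached in about 77% of trials at 9.1 months. The cost would be precision on a secondary endpoint with no stated hypothesis or threshold, and the primary response-rate analysis would be largely unaffected.

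The sizes rest on exponential survival, uniform 6-month accrual and no loss to follow-up. The conclusion itself rests on the reading of the text and on the expectation that the sponsor follows patients for the full 12 months.
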